14.0 Risks and Benefits

14.1 Risks of Harm:

Identify all research-related risks of harm to which the subject will be exposed for each research procedure or intervention as a result of participation in this study. Consider the risks of breach of confidentiality, psychological, legal, social, and economic risks as well as physical risks. Do not describe risks from standard care procedures; only describe risks from procedures done for research purposes

Risks: Participation in this research study will involve treatment with physical and occupational therapy, acupuncture, chiropractic, yoga with or without medical massage and biofeedback. All of these modalities are low risk treatments, and these risks will be explained to potential subjects during the informed consent process.

Psychological distress: It is possible that some participants will experience psychological distress during pain therapies. This risk will be mitigated by attempting to make the therapies as comfortable as possible for each participant. It is not anticipated, but in the event any psychological/emotional distress occurs, the PI will stop the therapy, and soothe, calm, and assist the participant in regaining control before the therapy continues. In the event that this is not effective, the PI will refer the participant to the appropriate primary care provider or a health care professional at Madigan Army Medical Center.

Loss of Confidentiality: This risk will be mitigated using several precautions discussed in Confidentiality of Research Data.

14.2

Measures to Minimize Risks of Harm (Precautions, safeguards):

For each research procedure or intervention, describe all measures to minimize and/or eliminate risk of harms to subjects and study personnel

The therapeutic approach to treatment modalities will be adjusted as needed based on each patient's response to therapy. For example, if one chiropractic technique increases pain, other techniques will be employed to improve response. While mild muscle soreness is common in FR programs, it is unlikely that injury will occur. If acute injuries do occur, the patients will be managed by IPMC medical staff or their primary care team within MAMC at no cost to the study participant.

This risk of psychological distress will be mitigated by attempting to make the therapies as comfortable as possible for each participant. It is not anticipated, but in the event any psychological/emotional distress occurs, the PI will stop the therapy, and soothe, calm, and assist the participant in regaining control before the therapy continues. In the event that this is not effective, the PI will refer the participant to the appropriate primary care provider or a health care professional at Madigan Army Medical Center.

The risk of loss of confidentiality will be mitigated using several precautions discussed in Confidentiality of Research Data.

14.3

Confidentiality Protections (for research records, data and/or specimens):

Describe in detail the plan to maintain confidentiality of the research data, specimens, and records throughout the study and at its conclusion (e.g., destruction, long term storage, or banking). Explain the plan for securing the data (e.g., use of passwords, encryption, secure servers, firewalls, and other appropriate methods). If data will be shared electronically with other team members/collaborators outside the institution, describe the method of transmission and safeguards to maintain confidentiality. Explain whether this study may collect information that State or Federal law requires to be reported to other officials or ethically requires action, e.g., child or spouse abuse

Confidentiality of the Data.

Complete confidentiality cannot be promised, particularly for military personnel, because information bearing on health or illegal activities may be required to be reported to appropriate medical or command authorities.

The research records may be looked at by staff from Madigan Army Medical Center's Department of Clinical Investigation and the Institutional Review Boards (IRB) of Madigan Army Medical Center. The records may be looked at by staff from the Army Clinical Investigation Regulatory Office (CIRO), Army Human Research Protections Office (AHRPO), the study sponsor, and other government agencies that provide oversight for human subject protection as part of their duties.

All identifying information will be excluded and/or removed from study documents to the greatest extent possible. Each individual screened for participation will be assigned a unique study identification number. The study identification number links the individual to study documents and will be used to

help prevent disclosure of identifiable personal information. Study identification numbers will be maintained by the PI on a master list that will be stored separately from other study documents in a locked cabinet.

Study documents will be stored in locked cabinets and on secure servers. Study documents in use will be managed on password protected computers with password protected storage devices with documents and files that do not contain identifiers.

Database and master list will be stored on a password protected secure computer in the research coordinator's office. Master list will also be stored on password protected Excel spreadsheet, accessible only to research coordinator, research assistant and PI. Master list will not leave Madigan. The de-identified data will only be shared among the PI, AI, and the collaborators of this study. Only the PI, research coordinator, research assistant, and clinical staff involved in study visits will have access to forms containing PHI, these forms will be stored in a locked file cabinet in the research office and will not leave Madigan. PASTOR Data will be kept on a secure server. All data will be de-identified before being transferred to an electronic database at the University of Washington, on the 14th floor of the Health Sciences Building for analysis. Data will be transferred via secure methods, and subject data will not be linked to other databases. Only authorized persons actively involved in conducting the study, monitoring safety and evaluating study results will have access to the records.

The following data types will be compiled by the Defense Health Agency Clinical Support Programs Solution Delivery Division (DHA/SDD) through an approved data sharing agreement. The process for data management and de-identification of these data is explained in the data management section.

- Demographic information for study subjects
- Prescription data
- Opioid dosage and associated risk of serious respiratory depression as reported in the Defense Health Agency Opioid Registry
- Military medical readiness as reported in the Army Medical Protection System (MEDPROS)
- Number of clinical encounters and number and type of interventional procedures which each subject underwent in the Madigan Interdisciplinary Pain Management Center during the study period
- Diagnosis codes

Once data collection is complete, the master list will be destroyed.

The PI will manage, maintain, and secure all study documents and materials. The PI as the primary control point, combined with a small supporting research team, will help protect against disclosure.

14.4 Potential Benefits:

Describe any real and potential benefits of the research to the subject and any potential benefits to a specific community or society

If the individuals in the research are considered experimental subjects (per 10 USC 980), and they cannot provide their own consent, the protocol must describe the intent to directly benefit all subjects

For us as a nation to continue achieving health care advances that enhance the health of military service members and promote a fit and ready force, it is important that service members be able to participate in ethically sound research. These health advances are also important for society in general. Military health care research is often found to be relevant to civilian health care, particularly in the management of pain and trauma. The potential benefits of participation in these treatment modalities include pain relief, improved functional improvements and improved mood. As the risks for the proposed study are minimal, the potential benefits outweigh the risks.

14.5**Privacy for Subjects:**

Describe the measures to protect subject's privacy during recruitment, the consent process, and all research activities, etc.

Prospective study subjects will be informed about the study in a private area of the clinic or by telephone from the research staff office. A Request for Partial Waiver of HIPAA Authorization for Recruitment will be requested to permit the research assistant or research coordinator to review potential subjects' medical records to ensure there are no disqualifying conditions, such as impending surgery or unstable psychological status. This review of medical records is required for all FR participants, regardless of study participation status. Baseline and outcomes data that will be collected from study participants are the same data that are collected from all IPMC patients who participate in the functional restoration (FR) program, regardless of status of research project participation and are used to guide therapy. The IPMC has been using these or similar measures since the FR program started in 2013. Measures to ensure confidentiality are discussed in section 7.3.3.

14.6**Incidental or Unexpected Findings:**

Describe the plan to address incidental findings and unexpected findings about individuals from screening to the end of the subject's participation in the research. In cases where the subject could possibly benefit medically or otherwise from the information, state whether or not the results of screening, research participation, research tests, etc., will be shared with subjects or their primary care provider. State whether the researcher is obligated or mandated to report results to appropriate military or civilian authorities and explain the potential impact on the subject

The study is low-risk; therefore we do not anticipate any serious adverse events.

The most likely adverse event associated with participation in this study is mild-self-limited muscular soreness in the initial days of functional restoration, as each participant begins the reconditioning process. This is anticipated to occur in 75% of participants and to resolve within one week of onset. These complaints will be addressed and managed by the IPMC physical and occupational therapy teams.

This intervention qualifies as a Phase II clinical trial. We have developed a data and safety monitoring plan, which is outlined below. The plan includes routine monitoring of adverse events by the PI and study staff.

Monitoring study safety. Study safety will be monitored quarterly and includes auditing a random selection of 5% of cases for compliance with IRB requirements, conformance with informed consent requirements, verification of source documents and investigator compliance. Conference calls or in-person meetings are scheduled quarterly or on an as-needed basis with all data collectors and providers to review protocol and possible study safety issues. Booster sessions on administering the protocols will be given if needed. Each study team member will also receive a personal performance update with comments on protocol adherence and completeness of data. All violations of protocol are noted.

Identification of Adverse Events. [name] will be responsible for monitoring the internal review of adverse events. Adverse events will be identified by either intervention facilitators or study staff and reported to either [name] within 72 hours of occurrence, who will determine whether the event qualifies for reporting to the IRB.

To help ensure consistency in reporting, adverse events and safety alerts will be tracked using a standardized form that records the date of the event, attribution of the event (e.g., intervention-related or external situation, such as a death in the family), resolution of the event (whether resolved or controlled), and date of resolution.

The format of the form was validated during our previous work and is shown in Table 1.

Table 1: Adverse Event Reporting Form with Sample Text Entries

Event	Date	Severity	Attribution	Operational definition	Resolution

Sample entry:

Suicidal behavior	XXX	Serious	Not intervention-related/ assessed at baseline	Any risk or attempt to inflict serious bodily harm to self that may result in death	-Referral to mental health practitioner -Event is ultimately resolved when the mental health practitioner determines that there is no further risk
-------------------	-----	---------	---	---	---

In handling adverse events, project staff will follow the general principles devised for developing a safety plan for behavioral trials. Namely:

1. Adverse events queries should include domains plausibly affected by the interventions being tested. A primary question in defining adverse events in behavioral trials pertains to potential risks or negative events that can occur as a result of a specific intervention or of study procedures. Behavioral intervention research needs to also address behavioral, psychological, legal, economic, and social events, as these domains could be affected by the intervention being tested. To understand the adverse events or unexpected problems that can occur as a result of a behavioral intervention, it is important to monitor what the process of change will entail. These changes can be inherent to the mechanism of action of intervention under study. For example, addressing one's fears or challenging false beliefs may increase the risk of suicidal thoughts or behavior. The research team will keep detailed field notes about each visit and phone call.
2. Monitoring should attempt to assess relationships between intervention and adverse events.
3. Systematic monitoring is essential to identifying unexpected events. In addition to immediately addressing a potential adverse event, the research team will discuss all active cases in depth during the weekly research team meetings, and any potential adverse events, safety alerts, or other concerns will also be discussed.
4. Effective monitoring is a shared responsibility that includes multiple stakeholders, namely the research team, the Advisory Committee, and the IRBs.

All events will be discussed on a monthly basis during research team meetings, and any adjustments to the intervention or study protocol will be negotiated and agreed upon by the team.

15.0

Study Monitoring

15.1 Data Monitoring Plan:

Describe the plan to monitor the data to verify that data are collected and analyzed as specified in the protocol. Include who will conduct the monitoring, what will be monitored and the frequency of monitoring

Study safety will be monitored quarterly and includes auditing a random selection of 5% of cases for compliance with IRB requirements, conformance with informed consent requirements, verification of source documents and investigator compliance. Conference calls or in-person meetings are scheduled quarterly or on an as-needed basis with all data collectors and providers to review protocol and possible study safety issues. Booster sessions on administering the protocols will be given if needed. Each study team member will also receive a personal performance update with comments on protocol adherence and completeness of data. All violations of protocol are noted.

15.2 Safety Monitoring Plan:

Describe the plan to monitor the data to ensure the safety of subjects

Study safety will be monitored quarterly and includes auditing a random selection of 5% of cases for compliance with IRB requirements, conformance with informed consent requirements, verification of source documents and investigator compliance. Conference calls or in-person meetings are scheduled quarterly or on an as-needed basis with all data collectors and providers to review protocol and possible study safety issues. Booster sessions on administering the protocols will be given if needed. Each study team member will also receive a personal performance update with comments on protocol adherence and completeness of data. All violations of protocol are noted.

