If the physician determines that the patient is a candidate for the FR program and the patient is willing to commit to this intensive treatment approach, the patient is evaluated by a physical therapist to measure baseline functional status and to determine if he/she has the physical stamina to successfully participate in FR.

The research coordinator or research assistant will perform a brief screen of each potential subject's medical record to determine if he/she has any excluding conditions. If the potential subject has no excluding conditions, the research coordinator or research assistant will meet with him/her to explain the study and to request their consent for study participation. The commanding officer for each subject will be contacted and asked to approve the subject's absence from work as needed for the 6-9 week program.

Randomization

Then, each patient will be randomized to one of two treatment groups: the standard FR program or the FR + integrative modalities (IM) program. Because it is assumed that some participants who randomize to the standard FR program may be interested in IM, the standard FR group will be offered the option of IM following completion of the FR program. The components of the intervention and control treatments are shown in Table 2.

Standard care is comprised of twice weekly health psychology group therapy, twice weekly physical therapy and once-twice weekly occupational therapy during the three weeks prior to FR. Participants on chronic opioid therapy will also be seen by a clinical pharmacist for evaluation for opioid taper. The IM program is comprised of twice weekly acupuncture and chiropractic and once weekly yoga and myofascial release instruction by massage therapist. If indicated, biofeedback and individual massage may also be used. The FR program includes four full days of therapy per week for three weeks. Each FR treatment day will include approximately four-hours of physical activity and one hour each per day of health psychology group therapy and an educational session. Examples of the daily schedules for SC, IM and FR is shown in Figure 2. In an effort to meet enrollment targets, patients who are otherwise eligible for FR program participation but cannot commit to 4 full days of therapy for a three-week period will be given the option of 2 full days of therapy over a six-week period for the same number of contact hours.

Table 2. Intervention and Standard Care

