Chronic Pain Acceptance Questionnaire (CPAQ8)⁷⁶

Canadian Occupational Performance Measure (COPM)⁸¹

Roland-Morris Disability Questionnaire⁸⁰

Opioid utilization screener*

- Current opioid regimen
- Duration of pain and of opioid treatment
- Morphine equivalent dose
- Pain relief from opioids**

*Data on utilization and dosage are electronically extracted by PASTOR from the CHCS Electronic Medical Database.

**Patient self-reports pain relief if applicable.

Based on six months of experience with use of PASTOR at the Madigan Interdisciplinary Pain Management Center, the time required to complete this study's PASTOR measures is expected to be

approximately 20 minutes at baseline and 15 minutes at each follow-up time point. Because the PASTOR platform is a secure, web-based system, participants will have the option of completing PASTOR from the convenience of their homes. The psychometrics of PASTOR are discussed in section 7.3.4.

Upon completion of a PASTOR assessment, a three-page report is generated (see Section 6: Surveys, Questionnaires, and Other Data Collection Instruments – PASTOR) that summarizes all domains measured and displays them longitudinally once there are two or more assessments completed. Raw data will be stored in the PASTOR outcomes registry and made available to the research study after patient identifiers have been removed. It is planned that PASTOR will eventually include other validated measures relevant to pain, including the Patient Activation Measure, Pain Catastrophizing Scale, Tampa Scale for Kinesiophobia, Pain Self-efficacy Questionnaire and Chronic Pain Acceptance Questionnaire. Until these measures are added to electronic PASTOR assessment tool, these additional questionnaires will be administered in paper form at the same intervals that PASTOR is administered.

In February 2016, the Army Functional Restoration Workgroup determined that the Rolland-Morris Disability Score and the Canadian Occupational Performance Measure should be among the standardized outcome measures used by all Army FR programs, so these outcome measures are also included.

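### Adverse events are found through staff contact, which differs by arm, and no fixed adverse event question is asked of both arms, so comparing events by arm would mix detection with harm

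*Combined protocol and SAP*

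**What the plan says.** **Capture.** Section 14.6 gives the rule: "Adverse events will be identified by either intervention facilitators or study staff". It adds: "The plan includes routine monitoring of adverse events by the PI and study staff". Events are reported within 72 hours and logged on a standard form that records attribution. The principles in the same section include "Adverse events queries should include domains plausibly affected by the interventions being tested", that monitoring should be systematic, and that it should try to relate events to the intervention. On practice, the section says "The research team will keep detailed field notes about each visit and phone call", and all active cases are discussed at weekly team meetings. The quarterly monitoring in 15.1 and 15.2 audits consent, source documents and compliance. It puts no question to patients.

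**Assessments.** Section 10.1 schedules five assessments for all patients: baseline, end of pre-FR, end of FR, and 3 and 6 months after FR. Neither Table 3 (10.1) nor Table 8 (10.2) lists an adverse event item. For the electronic questionnaire, "participants will have the option of completing PASTOR from the convenience of their homes".

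**Treatment.** Both arms receive standard care before FR. For the arm given more, section 10.1 says: "The IM program is comprised of twice weekly acupuncture and chiropractic and once weekly yoga and myofascial release instruction by massage therapist". FR is the same for both arms. Afterwards, controls are offered the IM sessions as an option.

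**Expected events.** Section 14.2 foresees that IM may worsen pain: "if one chiropractic technique increases pain, other techniques will be employed to improve response". The only expected event with a frequency in 14.6 is muscle soreness early in FR (75%). Section 11.3 specifies no adverse event analysis.

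**The concern.** The randomised difference between the arms is a set of extra sessions with treatment providers, and treatment providers are one of the two named sources of adverse event reports. The other written routes, notes on visits and calls and team discussion of cases, also depend largely on what contact brings to light. Without a question put to both arms at the same times, the chance that an event is recorded can differ by arm even when the chance that it happens does not.

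At stake is the plan's own aim in 14.6 of relating events to the intervention. Soreness in FR says little about IM, because both arms receive FR. The informative period is the pre-FR stage, where contact differs most. After FR the imbalance can run the other way.

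**Working it through.** The plan states no contact ratio, so there is no figure to reproduce. The inputs are the session frequencies in 10.1 (Randomization) and the hours in Table 2. I take the foam roller class in Table 2 to be the myofascial release instruction in the text.

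**Pre-FR sessions over 3 weeks**
- Controls: psychology 2 + physical therapy 2 + occupational therapy 1 to 2 = 5 to 6 per week; × 3 = 15 to 18.
- IM adds acupuncture 2 + chiropractic 2 + yoga 1 + foam roller 1 = 6 per week; × 3 = 18.
- IM total: 33 to 36. Ratios: 33/15 = 2.2 and 36/18 = 2.0.
- With biofeedback (1 per week) and massage (0.5 per week) if indicated, IM has 37.5 to 40.5: 37.5/15 = 2.5 and 40.5/18 = 2.25.

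**Pre-FR hours over 3 weeks**
- Controls: (2 + 2 to 3) × 3 = 12 to 15.
- IM adds (0.5 + 2 + 1 + 1) × 3 = 13.5, giving 25.5 to 28.5. Ratios: 25.5/12 = 2.1 and 28.5/15 = 1.9.

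**Through the end of FR.** FR hours are taken as 72 (6 h × 12 days, Table 2) to 96 (the maximum in 10.1).
- Smallest excess: (15 + 13.5 + 96)/(15 + 96) = 124.5/111 = 1.12.
- Largest, with the if-indicated items (17.25 h): (12 + 17.25 + 72)/(12 + 72) = 101.25/84 = 1.21.
- Within FR itself the ratio is 1.0.

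**After FR.** Treatment sessions in the IM arm: 0 described. In controls: 0 if the option is declined, about 18 core sessions (13.5 h) if accepted. Uptake is not given. Both arms have the 3- and 6-month assessments.

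**What doubled contact could do to counts.** This is an assumption, not a figure in the plan. Suppose an event present throughout the stage is noticed at each session independently with probability p, controls have 15 sessions and IM patients 30. Detection in controls is d = 1 − (1 − p)^15 and in IM is 1 − (1 − d)². With equal true rates the apparent ratio is [1 − (1 − d)²]/d = 2 − d.

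| p per session | d in controls | Apparent IM:control ratio |
|---|---|---|
| about 1.5% | 0.20 | 1.8 |
| about 3% | 0.40 | 1.6 |
| 10% | 0.79 | 1.2 |
| 20% | 0.96 | 1.04 |

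An event that starts midway has about half the sessions left, so the p needed for a given d roughly doubles.

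**What existing measures cover.** Pain intensity, pain interference, depression, anxiety and anger are scored in both arms at all five assessments (Table 3), and section 10.2 mentions five health care utilization items in PASTOR. These would show sustained worsening at an assessment in either arm. They do not record a new injury, a flare that needed care and then settled, or another discrete event.

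**The case against.** The strongest reply is that no planned inference is affected. Section 11 compares no adverse events by arm, and the reporting form attributes events one by one. That stands: the bias arises only if counts are compared. But 14.6 sets the aim of relating events to the intervention, and a count by arm is the usual way to do that.

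Four stronger readings are tempting, and the documents do not support them.
- A reader might infer that treatment staff are the main source. Section 14.6 names facilitators and study staff without ranking them, and the PI also monitors.
- A reader might infer that patients are not seen after FR. Only treatment sessions end. Both arms have two further assessments, and Table 8 lists functional tests by a physical therapist, apparently at those times too (its layout is broken in the text).
- A reader might infer that counts would show contact and not harm, or that the trial could say nothing about harm from IM. Extra sessions are also extra exposure, contact is equal in FR, and pain and mood are scored in both arms.
- A reader might infer that the favourable risk statement in 14.4 depends on these counts. It is a prospective judgement that rests on the modalities being low risk.

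The size is also open to challenge. Ratios of 1.6 to 1.8 need only 1.5% to 3% detection per session, which is low for patients seen 15 to 18 times in three weeks. At 10% or more the ratio is 1.2 or less.

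**Conclusion.** The concern holds as a gap in safety reporting. Capture depends on contact, no arm-neutral question is scheduled, and the plan does not carry out the queries that its own principles call for. Scheduled pre-FR contact is about double in IM (2.0 to 2.2 times by core sessions, 1.9 to 2.1 by core hours), equal in FR, and afterwards possibly greater in controls, depending on uptake that the documents do not give. A by-arm comparison would therefore be confounded by detection, in opposite directions before and after FR.

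The contact figures follow from the schedule. The apparent ratios rest wholly on the assumed detection model and probably lie nearer its lower end. The co-primary analyses are untouched. This is a cheap improvement, not a flaw in the main comparison.

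**What to change.** Add one fixed adverse event item to the paper packet already given to both arms at each PASTOR interval (10.1): new or worse injury, pain flare needing care, or psychological event since the last assessment. The baseline version needs its own recall window and serves as the pre-treatment reference. The later assessments fall at the ends of pre-FR and FR and during follow-up, so the answers map onto the three phases.

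In section 11.3, specify a table of these answers by arm and phase (pre-FR, FR, post-FR), with the number answering in each cell, and show staff-identified events separately. The contact hours tracked under 10.12 can be reported beside it to show the opportunity for detection.

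Diagnosis codes, which 14.3 already lists for extraction, can serve as a supporting check. Do not compare the encounter counts listed there ("Number of clinical encounters and number and type of interventional procedures which each subject underwent in the Madigan Interdisciplinary Pain Management Center during the study"): IM sessions are themselves encounters in that clinic, so the counts differ by design, and injuries managed in primary care (14.2) would not appear.

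The cost is one or two more items for patients on an existing form, to which the protocol already added one or two questions at the end of FR, plus one table. The small downside is more minor events recorded. No extra visits are needed. Sections 9.4 and 11.3 describe some data collection in the past tense. Assessments already completed cannot be recovered this way, and for those any by-arm table should carry the detection caveat.

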16.0 Reportable Events

16.1 Reportable Events:

Consult with the research office at your institution to ensure requirements are met

- Describe plans for reporting expected adverse events. Identify what the expected adverse events will be for this study, describe the likelihood (frequency, severity, reversibility, short term management and any long term implications of each expected event)
- Describe plans for reporting unexpected adverse events and unanticipated problems. Address how unexpected adverse events will be identified, who will report, how often adverse events and unanticipated problems will be reviewed to determine if any changes to the research protocol or consent form are needed and the scale that will be used to grade the severity of the adverse event

All unanticipated problems involving risk to subjects or others and all serious adverse events or subject deaths related to the research will be reported within 48 hours of the research team's knowledge of the event to the MTF IRB. Submission of a complete written report in IRBNet will follow the initial notification within 10 working days.

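### For reportable events the research team learns of within 24 hours of occurrence, the 72-hour internal reporting limit can outlast the 48-hour IRB deadline

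*Combined protocol and SAP*

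**What the plan says.** Section 14.6, under Identification of Adverse Events, sets the internal route. "Adverse events will be identified by either intervention facilitators or study staff and reported to either" a recipient whose name has been removed, "within 72 hours of occurrence, who will determine whether the event qualifies for reporting to the IRB". The limit applies to adverse events in general; no shorter one is given for serious or unanticipated events.

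Section 16.1 sets the external route. It covers "All unanticipated problems involving risk to subjects or others and all serious adverse events or subject deaths related to the research". These "will be reported within 48 hours of the research team's knowledge of the event to the MTF IRB". A second step follows: "Submission of a complete written report in IRBNet will follow the initial notification within 10 working days".

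The nearest thing to a faster internal route is in the monitoring principles of section 14.6: "In addition to immediately addressing a potential adverse event, the research team will discuss all active cases in depth during the weekly research team meetings". That asks for prompt handling and weekly discussion, but sets no time for telling the deciding role.

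**The concern.** The internal step comes before the reportability decision, and that decision comes before the IRB is told. The internal step should therefore finish well inside the IRB window. As written it may finish after the window has closed.

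What is at stake is timely IRB notice of the events for which the 48-hour rule was written. Treatment is delivered in person, with about four hours of physical activity on each functional restoration day (section 10.1), so an injury in a session could be seen as it happens. Randomisation, endpoints and analysis are not affected.

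**Working it through.** No sample size, power or alpha figure is involved. The check is a timeline.

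**Inputs**
- Internal limit: 72 hours, counted from occurrence (section 14.6).
- IRB limit: 48 hours, counted from the research team's knowledge (section 16.1).
- K: hours from occurrence to the research team's knowledge. The documents give no value, so it is varied below.

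**Formulas**, with time zero at occurrence
- IRB deadline = K + 48.
- Latest permitted internal report = 72.
- Possible overrun = 72 − (K + 48) = 24 − K, where positive.
- The internal limit can outlast the IRB deadline when K + 48 < 72, that is K < 24.

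**Results**

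| K (h) | IRB deadline (h) | Internal limit (h) | Consequence |
|---|---|---|---|
| 0 (witnessed) | 48 | 72 | overrun up to 24 h |
| 12 | 60 | 72 | overrun up to 12 h |
| 24 | 72 | 72 | limits coincide; no time left to decide |
| 48 | 96 | 72 | internal limit falls 24 h before the IRB deadline |

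The overruns are counted to the moment the deciding role is told. Time taken for the decision itself would add to them.

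**Does other text close the gap?**
- Section 16.1 starts its clock at knowledge of the event, not at its classification as reportable. The time before the decision therefore counts against the 48 hours.
- The written report due in 10 working days follows the initial notification and does not extend it.
- The weekly and monthly team discussions in section 14.6 set no internal reporting time.

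**Whose knowledge starts the 48 hours?** Research team is not defined. Section 14.6 has the research team keep field notes on visits and calls, which is staff-level work, so study staff naturally belong to it. Facilitators are less clear: section 14.3 lists clinical staff at study visits separately from the research coordinator and assistant. If facilitators fall outside the team, an event that only they see may start the 48-hour clock when they report it, and no breach follows on that route.

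**The case against.** The strongest reply is that the two rules do not contradict each other. Section 14.6 gives an outer limit for any adverse event, including the mild soreness expected in 75% of participants. Section 16.1 gives a tighter rule for a small subset. Staff who pass on a serious event at once satisfy both, and section 16.1 can be read as the special rule that governs such events. Section 14.6 also says that no serious adverse events are anticipated.

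Part of this stands. The rules can be met together, and the events concerned should be few. But reading section 16.1 as the special rule does not shorten the internal step: the person who applies section 16.1 may not hear of the event until hour 72. Nor does a low expected frequency settle it, since reporting rules exist for the unexpected. The sample form in section 14.6 uses a serious event, suicidal behavior, as its illustration, although there as unrelated to the intervention.

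A reader might infer more than the documents support:
- *That 72 against 48 hours is a like-for-like contradiction.* It is not, because one clock runs from occurrence and the other from knowledge. From K = 24 upward the internal limit no longer runs past the IRB deadline.
- *That any serious event seen by staff is exposed to a 24-hour delay.* Section 16.1 limits serious events and deaths to those related to the research, and 24 hours is the maximum, reached only at K = 0.
- *That the conflict applies equally to facilitators.* The undefined term leaves that open.
- *That safety oversight rests on the investigator and staff alone.* Section 14.6 also names the Advisory Committee and the IRBs as sharing the monitoring.

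**Conclusion.** The point holds within limits. For an event covered by section 16.1 that the research team learns of less than 24 hours after it occurs, full compliance with section 14.6 can miss the IRB deadline by up to 24 − K hours, so by at most 24. At K = 24 there is no overrun but also no time to decide. Beyond that, the internal limit alone causes no breach.

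This rests on two readings: that study staff are part of the research team, and that the 48 hours run from knowledge of the event itself. Both follow the plain sense of the text. Whether facilitators are included cannot be settled from the documents.

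The effect is on the timing of IRB notification. It does not mean that participants go without immediate attention, and it does not touch the trial's estimates. It is worth correcting because a written procedure that is followed exactly should not be able to breach another.

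**What to change.** Reconcile sections 14.6 and 16.1:

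1. For every event that section 16.1 covers, count the internal step from staff awareness and require it to end inside the 48-hour IRB window, with time left for the reportability decision. This must include unanticipated problems that are not serious. A split drawn only between serious and non-serious events would leave those under both limits.
2. State whether intervention facilitators count as research team for the start of the 48-hour clock.
3. Keep the 72-hour limit only for events outside section 16.1.

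Counting from awareness also helps with events first learned of at the 3- or 6-month assessment, which may already be more than 72 hours old.

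The cost is a sentence or two in section 14.6, a definition of research team, and a reminder to staff. No data collection or analysis changes.
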